15.1.2 Adverse Drug Reactions

Adverse drug reactions are concern noxious and unintended responses to a medicinal product within adverse events.

15.1.3 Serious Adverse Events (SAE)

A Serious Adverse Event (experience) or reaction is any untoward medical occurrence that at any dose:

- (a) Results in death.
- (b) Is life-threatening.

NOTE: The term "life-threatening" in the definition of "serious" refers to an event in which the patient was at risk of death at the time of the event; it does not refer to an event which hypothetically might have caused death if it were more severe.

- (c) Requires inpatient hospitalization or prolongation of existing hospitalization. The following are not considered hospitalizations for the purposes of assessing seriousness:
 - Emergency room visits less than 24 hours.
 - Hospitalizations for preplanned procedures.
 - Hospitalization for study-related treatment and procedures.
- (d) Results in persistent or significant disability or incapacity.
- (e) Is a congenital anomaly/birth defect.
- (f) Is any other important medical event.
 - Medical and scientific judgment should be exercised in deciding whether expedited reporting is appropriate in other situations, such as important medical events that may not be immediately life-threatening or result in death or hospitalization but may jeopardize the patient or may require intervention to prevent one of the other outcomes listed in the definition above. These should also usually be considered serious.
 - Examples of such events are intensive treatment in an emergency room or at home for allergic bronchospasm; blood dyscrasias or convulsions that do not result in hospitalization; or development of drug dependency or drug abuse.

Serious adverse events must be reported to Taiho Drug Safety or designee within 24 hours from the time the investigator first becomes aware of the SAE. The SAE reporting process and contact information for reporting SAEs are provided in the CRF and SAE Completion Guidelines.

After the initial SAE notification to Taiho Drug Safety or designee, follow-up SAE information will be submitted each time that important follow-up information (e.g., diagnosis, outcome, causality assessment, results of specific investigations) becomes available.

All SAEs within the follow-up window (e.g., within 30 days after the last dose of study medication or until the start of new anti-tumor therapy, whichever is earlier) established in the protocol will be reported to Taiho Drug Safety or designee.

If serious medical occurrences including deaths outside the follow-up window established by the protocol are reported to or observed by the investigator that he/she believes are related to the administration of the investigational product, it is the investigator's responsibility to report this occurrence to Taiho Drug Safety or designee.

15.1.4 Disease Progression

Disease progression is not an acceptable AE term. In cases of disease progression the relevant signs, symptoms and complications should be reported as an AE unless they meet the serious criteria. If any of the signs, symptoms and complications meets any of the serious criteria, they should be reported as an SAE. In both cases it should be indicated whether the signs, symptoms and complications are related to disease progression.

In cases of death due to clinical disease progression, clinical disease progression may only be reported as an SAE term if none of the relevant signs or symptoms support a fatal

outcome.

Radiological disease progression without relevant signs, symptoms and complications will not be reported as an AE or SAE.

15.1.5 Pregnancy

If a patient becomes pregnant while in the study, the study treatment must be immediately discontinued. Pregnancy information for a female patient or for the female partner of the male patient should be reported within 24 hours from the time the investigator first becomes aware of a pregnancy or its outcome. This should be performed by completing a Pregnancy Form and emailing or faxing it to Taiho Drug Safety or designee.

New and/or corrected information regarding the pregnancy obtained after submitting the Pregnancy Form must be submitted by emailing or faxing an updated Pregnancy Form to Taiho Drug Safety or designee.

If outcome of the pregnancy is a stillbirth, congenital anomaly/birth defect, or a serious event in the mother, report as an SAE to Taiho Drug Safety or designee.

15.1.6 Other Information

Any information about overdose, or medication error, which was defined below, should be forwarded to the sponsor regardless of whether it is associated with an adverse event (even if not fulfilling seriousness criterion).

- Overdose: Administration at a dose above the dose specified in “section 10.1 Dose, administration method, and administration period”;
- Medication error: Any errors in administration of the study treatment, including the wrong agent, wrong route of administration, wrong dose/dosing interval, and accidental ingestion;

15.1.7 Breaking the Study Blind

This is an open-label study. Both investigators and patients will be aware of which treatment regimen the patient is receiving, TAS-118/L-OHP or S-1/CDDP.

15.2 Laboratory Evaluations

15.2.1 Reporting and Evaluation of Laboratory Test Results

Laboratory tests are to be performed as required per protocol. All laboratory values that are out of the normal range are to be evaluated for their clinical significance before exposing the patient to the next dose of study medication.

The laboratory must provide normal reference ranges.

Any laboratory abnormality that is clinically significant, e.g., results in delay of study

medication dosing, study discontinuation, requires treatment due to abnormal values, or is considered by the investigator to be medical important, must be reported as an AE, unless it is considered a supporting lab to a clinical diagnosis that is already reported as an AE. All laboratory data will be analyzed using NCI CTCAE grade criteria (version 4.03).

15.2.2 Repeat Testing

Repeat the evaluation of any clinically significant laboratory test, as clinically indicated, until the value returns to the baseline level or clinically stabilizes, or until new anti-tumor therapy is given.

15.3 Physical Examination and Performance Status

Perform physical examinations and performance status evaluations as described in the Study Procedures section of the protocol. If changes are observed, determine whether they meet the definition of an AE. Document all observations and evaluations.

15.4 Body Temperature, Blood Pressure and Body Weight

Verify and document body temperature, blood pressure (systolic/diastolic) and body weight. If a clinically significant change is observed, repeat the measurement as clinically indicated and evaluate for its clinical relevance and whether it meets the definition of an AE.

16. Statistical Analysis

The data obtained during this clinical trial will be analyzed following the details provided below. In addition to this document, we will also prepare a Statistical Analysis Plan (SAP), which will include further technical details and descriptions of the planned statistical analyses and summaries of the results.

16.1 Timing of Statistical analyses

Four analyses will be performed at the times of two interim analyses, time of primary evaluation, and time of final analysis as follows.

16.1.1 Interim Analyses

The Independent Data Monitoring Committee (IDMC) will perform two interim analyses. In order to evaluate the safety data, first interim analysis will be performed by the IDMC. At second interim analysis, the IDMC will evaluate the safety and efficacy data based on these analyses. The IDMC will propose whether the trial should stop earlier based on the results obtained to that point. Further details of the role and responsibility of IDMC and the review process are provided in the IDMC charter. The interim analyses will be performed with the data gathered up to following cutoff point.

(1) Data cutoff for the first interim analysis

- In safety analyses, the cutoff data will be defined on the basis of the date when 100 death events are confirmed.

(2) Data cutoff for second interim analysis

- The cutoff date for primary endpoint is the date when 219 death, which is the 50% required number of death events, are confirmed.
- In safety analyses, the cutoff data will be defined on the basis of the date when 219 death events are confirmed.

16.1.2 Primary Evaluation

The primary analysis will be performed when the cutoff date is determined, and CRFs, dispositions and adoptions of all patients are fixed again.

(1) Data cutoff for primary evaluation

- The cutoff date for primary endpoint will be set at the date when 491 death events are confirmed, representing the final number of events required.
- In safety analyses, the cutoff data will be defined on the basis of the date when 491 death events are confirmed.

16.1.3 Final Evaluation

At the end of the trial, statistical analyses will be performed using all the data gathered to this point.

16.2 Populations and Criteria for Handling Patient Data

16.2.1 Analysis Populations

The analysis populations are defined in Table 16.2.1-1.

The sponsor, in collaboration with the medical specialists, will determine the overall disposition of the patients if there are any problems except the following criteria for patient's disposition.

FAS will be included only in the primary analysis.

Table 16.2.1-1 Definitions of Analysis Populations

Analysis Population	Definition
Enrolled Population	All patients enrolled in this trial.
As Treated (AT) Population	Enrolled patients who received at least one dose of the study drug.
Full Analysis Set (FAS)	Patients in AT population who have gastric cancer at randomization.
Tumor Response (TR) Evaluatable Population	Patients in FAS population presenting measurable lesions (at least one target lesion), evaluated for tumor responses at least once during treatment with the study drug.

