14.1.2 Assessment of Overall Response

Assessments will be based on the definitions provided in Table 14.1.2-1 and Table 14.1.2-2 below.

Table 14.1.2-1 Time Point Response for Patients with Target (+/- Non-target) Disease

Target Lesions	Non-target Lesions	New Lesions	Overall Response
CR	CR	No	CR *
CR	Non-CR/Non-PD or Not all evaluated	No	PR
PR	Non-PD or Not all evaluated	No	PR
SD	Non-PD or Not all evaluated	No	SD
Not all evaluated	Non-PD	No	NE
PD	Any	Yes or No	PD
Any	PD	Yes or No	PD
Any	Any	Yes	PD

* For CR, tumor marker must have been under upper limit of normal.

Table 14.1.2-2 Time Point Response for Patients with only Non-target Disease

Non-target Lesions	New Lesions	Overall Response
CR	No	CR *
Non-CR/Non-PD	No	Non-CR/Non-PD
Not all evaluated	No	NE
Unequivocal PD	Yes or No	PD
Any	Yes	PD

* For CR, tumor marker must have been under upper limit of normal.

When no imaging/measurement is done at all at a particular time point, the patient is not evaluable (NE) at that time point. If only a subset of lesion measurements are made at an assessment, usually the case is also considered NE at that time point, unless a convincing argument can be made that the contribution of the individual missing lesion(s) would not

change the assigned time point response.

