14.1.3 Best Overall Response Assessment

The best overall response as per RECIST Criteria (version 1.1) is the best response recorded from the start of the study treatment until the end of tumor follow-up period. The confirmation of tumor response for CR or PR is not required, but the duration of SD (or Non-CR/Non-PD) is set as 6 weeks from randomization (the data may be collected within 1 week before or after the scheduled date).

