14.2 Overall Response Rate (ORR)

ORR is defined as the proportion of patients with the best overall response of CR or PR in tumor response evaluable population.

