3.2. Analysis Populations

A list of the name and definition of analysis populations is presented in Table 3-2.

If there are any problems with the inclusion of subjects in each analysis population except the criteria listed below, the sponsor will determine in which population the subject should be included before analysis in the discussion with the medical advisor.

Table 3-2 Definitions of analysis populations

Analysis populations	Definition
Enrolled population	All patients enrolled in this trial
As-treated (AT) population	Enrolled patients who received at least one dose of the study drug
Full analysis set (FAS)	Patients in AT population who have advanced gastric cancer at randomization
Tumor response-evaluable population	Patients in FAS population who have measurable lesions (at least one target lesion) at baseline and are evaluated for tumor responses at least once during treatment with the study drug

4. Timing of Analyses and Significance Level

In this study, two interim analyses were planned and implemented before the analysis for the primary evaluation. Based on the results of the two interim analyses and IDMC reviews, the timing of the analysis for the primary evaluation is defined in Table 4-1.

In the analysis for the primary evaluation, whether TAS-118/L-OHP is superior to S-1/CDDP with respect to OS will be tested in the FAS population. As the test method, a stratified log-rank test will be conducted according to the following allocation adjustment factors: measurable lesion (yes, no), ECOG PS (0, 1), and country (Japan, Korea).

Table 4-1 Timing of each analysis and significance level

	Timing of analysis	Significance level at sample size determination
First interim analysis	When the number of death events reaches 100 (Date: April 22, 2016)	Not tested
Second interim analysis	When the number of death events reaches 219 (Date: November 30, 2016)	0.305%
Analysis for the primary evaluation	When the required number of death events, 491, is confirmed	4.899%

These significance levels were calculated using the Lan and DeMets method (O'Brien-Fleming type) at the time of sample size determination. The significance levels to be spent will be recalculated in the interim analyses and the analysis for the primary evaluation. The procedures for recalculation are presented in Section "5.2.4.12 Log-Rank Test Using Recalculated α "

5. Endpoints and Common Considerations for Statistical Analysis

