5.1.1.4.1 ORR

Overall response rate is defined as the proportion of subjects with the best overall response of CR or PR in the tumor response-evaluable population.

$$\text{ORR (\%)}: (\text{CR} + \text{PR}) / (\text{Number of subjects in the tumor response-evaluable population}) \times 100$$

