5.2.1.2 Handling of Missing Data and Abnormal Values

No imputation of missing data will be performed. All data accepted at each time point will be used for the analysis. The proportion of subjects with adverse events and other proportions will be calculated using the analysis population as the denominator.

All data measured will be used for the analysis unless the cause of abnormalities is obvious, such as laboratory abnormalities caused by hemolysis during blood collection. If there are abnormalities to be

excluded from the analysis, these values will be identified, and the reason for exclusion will be justified.

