7.1. Efficacy Analyses

The following analyses will be conducted for the endpoints of antitumor activity in the tumor response-evaluable population and for PFS and TTF in the FAS population. For the selected endpoints, the same analyses will also be conducted by country.

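### ORR and DCR are estimated and tested only in patients evaluated at least once on treatment, and no specified analysis counts the unevaluated as non-responders

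*Protocol*

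**What the plan says.** Both documents build the set in the same way. Protocol section 16.2.1 takes FAS patients with at least one target lesion who were "evaluated for tumor responses at least once during treatment with the study drug". SAP section 3.2 (Table 3-2) takes those who "are evaluated for tumor responses at least once during treatment with the study drug".

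The endpoints are tied to that set:

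- Protocol section 14.2: "ORR is defined as the proportion of patients with the best overall response of CR or PR in tumor response evaluable population".
- SAP section 5.1.1.4.1: "Overall response rate is defined as the proportion of subjects with the best overall response of CR or PR in the tumor response-evaluable population". Section 5.1.1.4.2 gives DCR the same denominator. Protocol section 14.3 names no denominator for DCR, but section 16.3.3.1 places it in the same set.
- SAP section 7.1 specifies analyses "for the endpoints of antitumor activity in the tumor response-evaluable population". The tests are Fisher's exact test (protocol section 16.3.3.1) and, in SAP sections 7.1.1.2 and 7.1.1.3, also a stratified Cochran–Mantel–Haenszel test.

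On missing data, SAP section 5.2.1.2 states: "No imputation of missing data will be performed". It and protocol section 16.2.2 compute proportions over the whole population being analysed.

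The SAP repeats OS (section 6.2) and PFS (section 7.1.2) in the enrolled population. It specifies no wider-population repeat for ORR or DCR.

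Best overall response has a longer window than the entry condition. Under protocol section 14.1.3 it "is the best response recorded from the start of the study treatment until the end of tumor follow-up period", and SAP section 5.1.1.4 agrees. Patients who stop without progression continue to be scanned every 6 weeks (protocol sections 11.7 and 13.1.3).

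**The concern.** Entry to the analysis set is decided after randomisation and is related to outcome. Patients who die or stop before any on-treatment evaluation are unlikely to be responders, so removing them raises the observed rate. If the arms lose different shares, the randomised comparison is distorted towards the arm that loses more.

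Equal loss is not assured. The trial is open-label, and cycles last 2 weeks in arm A and 5 weeks in arm B against one 6-weekly scan clock that starts at randomisation. Nothing in the documents shows which arm would lose more.

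There is also a mismatch that needs no assumption about d. A patient first scanned after stopping treatment has a valid best overall response under protocol section 14.1.3, yet is outside the set in which that response would be counted.

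What is at stake is the credibility of two named secondary endpoints that are compared by formal tests. OS is not touched, and no alpha is allocated to ORR or DCR.

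**Working it through.** **No figure of the plan is in dispute.** The documents give no sample size or power for ORR or DCR. They also do not give the share of patients with measurable disease or the share never evaluated. What follows illustrates size under stated assumptions.

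**Who leaves the denominator.** Patients inside the set who are graded NE stay in and count as non-responders, because proportions use the whole set. Patients with measurable disease and no evaluation during treatment are outside it, and no section brings them back.

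**Inflation formula.** If all excluded patients are non-responders, observed rate = true rate / (1 − d), where the true rate is that among all measurable-disease FAS patients in the arm.

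**Equal loss of 1% to 10% (assumption).** The true ORR is assumed to be 56%, midway between the phase II rates of 46% and 66% in protocol section 2.4. The true DCR is assumed to be 85%.

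- ORR: 56/0.99 = 56.6%; 56/0.90 = 62.2%.
- DCR: 85/0.99 = 85.9%; 85/0.90 = 94.4%.

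**Loss derived from the design medians.** Inputs are medians of 19.33 and 14.5 months with exponential survival (protocol section 16.4), a first scan at 6 weeks, and the SAP's 30.4375 days per month.

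- t = 42/30.4375 = 1.380 months.
- d in arm A = 1 − exp(−ln 2 × 1.380/19.33) = 4.83%.
- d in arm B = 1 − exp(−ln 2 × 1.380/14.5) = 6.38%.
- ORR: 56/(1 − 0.0483) = 58.84% in A and 56/(1 − 0.0638) = 59.82% in B, a false gap of 0.98 points favouring control.
- DCR: 89.31% in A and 90.80% in B, a false gap of 1.48 points (from unrounded rates) favouring control.

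This is probably an upper guide to loss through early death. Patients need a life expectancy of at least 90 days, and extra scans are made when progression is suspected.

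**False-positive rates.** These come from exact binomial enumeration of Fisher's exact test (two-sided p ≤ 0.05), with equal true rates and 250 measurable patients per arm before exclusion (assumption).

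| Loss A / B | Analysed A / B | ORR: total (favours A, favours B) | DCR: total (favours A, favours B) |
|---|---|---|---|
| None | 250 / 250 | 4.25% (2.13, 2.13) | 3.80% (1.90, 1.90) |
| Half the design-median loss | 244 / 242 | 4.55% | 4.65% |
| Design-median loss | 238 / 234 | 5.11% (1.30, 3.81) | 7.05% (0.54, 6.51) |
| 8% / 3% (assumption) | 230 / 242 | 9.86% (9.51, 0.35) | 36.94% (36.94, 0.01) |

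In the last row the observed ORRs are 56/0.92 = 60.87% and 56/0.97 = 57.73%, a gap of 3.14 points. The observed DCRs are 92.39% and 87.63%, a gap of 4.76 points. At a true DCR of 75%, false significance favouring A is 18.73%. Reversing the losses reverses the direction.

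**Sensitivity of the design-median row.** With 200 to 300 patients per arm, ORR runs from 4.9% to 5.2% and DCR from 6.0% to 7.9%. A true ORR of 46–66% gives 4.5–5.1%. A true DCR of 75–90% gives 5.9–9.6%.

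**The case against.** The strongest reply is that this is a prespecified choice on which both documents agree, for secondary endpoints without alpha, analysed by assigned arm. That is true, and it limits the severity. It does not change the fact that the set is selected on a post-randomisation event.

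The large figures need an assumed imbalance. On the same set-up, a 2% against 1% loss gives total false-positive rates of 4.7% (ORR) and 5.1% (DCR), and 5% against 3% gives 5.2% and 8.4%. This stands: ORR is little affected by modest imbalance, and the exposure is mainly DCR.

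The direction is not certain either. Some excluded patients may have responded, or had stable disease, on a scan made after stopping. The 1/(1−d) formula ignores them. This also stands, but it is a second reason to bring these patients back.

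The loss may be narrower than the wording suggests. Protocol section 14.1.2 says "When no imaging/measurement is done at all at a particular time point, the patient is not evaluable (NE) at that time point", and section 14.1.1.3 grades a missing examination as NE, so an unscanned patient still on treatment might count as evaluated. Section 6.1.1 runs the treatment period until a discontinuation criterion is met, and SAP section 5.2.1.1.3 accepts any assessment up to day 50 for the first time point. These passages leave the term evaluated unclear. They do not restore patients who die or stop before any evaluation.

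Finally, best response, measurable-lesion counts and exclusions with reasons are tabulated by arm (SAP sections 7.1.1.1, 7.3 and 7.5), so a reader could approximate the wider rate. SAP section 9 also refers to a separate output plan, which is not available and might contain more. Neither changes the specified estimates and tests, and the denominator of a named secondary endpoint belongs in the SAP.

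**Conclusion.** The concern holds. In the protocol and SAP, ORR and DCR rest solely on a set defined by being evaluated during treatment, and no specified analysis keeps the unevaluated in the denominator. The entry condition also disagrees with the best-response window, whatever the size of d.

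The numerical effect cannot be fixed from the documents. In the one scenario tied to the plan's own medians it is negligible for ORR, moderate for DCR and conservative for the experimental arm. It becomes serious, above all for DCR, only if the arms lose clearly different shares, which the documents neither show nor exclude. These sizes assume that excluded patients are non-responders, 250 measurable patients per arm, and true rates of 56% and 85%. The change is one that should be made because it is cheap; the primary conclusion does not depend on it.

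**What to change.** Define the ORR and DCR denominator as all FAS patients with a target lesion at baseline according to the CRF (the rule in SAP section 5.2.2), by assigned arm. Classify those with no post-baseline assessment as NE, hence as non-responders. Keep the tumour response-evaluable set as a supportive analysis. Align its during-treatment entry condition with the window to the end of tumour follow-up, and state whether an unscanned patient still on treatment counts as evaluated.

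Record this as a documented revision under SAP section 8 and list it in section 1.3, where the change to the FAS definition is already recorded. The cost is one SAP revision and one extra table, with no new data. The downsides are slightly lower stated response rates and a recorded departure from the protocol's ORR population.
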